#### 13.2. Source Data

Site teams will keep a record linking study identifiers to local hospital numbers only for the duration of the study and stored on a local NHS database accessible to the clinical team only.

#### 13.3. Confidentiality

Potential participants will be identified by healthcare staff caring for neonates in postnatal areas. Neonates who meet inclusion criteria and do not meet exclusion criteria will be informed of the study and asked to participate. It will be made clear that their data will be pseudonymised whilst being used for study purposes.

Data will be pseudonymised at the point of collection by the local teams and analysed centrally by the core BiliNEST team. Participant healthcare records will be accessed by local staff to collect only the minimal data required as per the CRF tool. Whilst the QMUL REDCap database will hold the pseudonymised data from all sites, each individual unit will only be able to access their own data. Unique patient identifiers will be used for each patient, with three letters identifying the trust (e.g. RLH=Royal London Hospital, WHI=Whittington Hospital), followed by three numbers from 001. Local project leads will keep a record between pseudonymised study numbers and identifiable data (e.g. the participant's local hospital number), in case there is a need to re-examine the data. No patient identifiable information will leave the local Trust. Data will only be stored on secured password protected Trust

computers. Only pseudonymised data will be shared with the central research team via the encrypted database, RedCAP.

# 13.4. Record retention and archiving

No physical archiving will be required in light of the opt-out consent process for the quantitative data collection. Consent for qualitative data collection will be obtained electronically and stored on a QMUL-based secure server. Clinical data will be stored on a secure REDCap database, for no longer than 5 years.

# 14. Safety reporting

Due to the design of this study, no adverse events are anticipated and safety reporting will not occur. We do not anticipate any delay or change to routine clinical care for study participants. Should any clinical concerns be incidentally detected during study assessments, these will be escalated to the relevant clinical team via the normal pathways. For example, should a concern regarding the parental health e.g. a disclosure of low mood, this will be relayed to the midwife caring for the parent. If, for example, the baby is noted to have increased respiratory effort, this will be urgently relayed to the on call team to instigate investigation and management. Should any unexpected safety concern be raised by any member of the study team, this will be escalated to the core study team and CI, and the site clinical management team if appropriate and the site-specific adverse event protocol will be followed.

# 15. Monitoring and auditing

The Sponsor or delegate retains the right to audit any study, study site or central facility. In addition, any part of the study may be audited by the funders where applicable.

Local site leads will be responsible for on-site monitoring and ensuring that local data collectors are GCP trained and have study-specific training prior to patient recruitment. The study monitoring plan will include periodic source data verification and is to ensure participant safety, data integrity and compliance to the protocol and GCP as well as the UK policy framework for Health and Social Care Research.

# 16. Study committees

The BiliNEST study management group will consist of the CIs, PIs, statistician, study coordination team and parent representatives. This group will convene for 3-monthly progress meetings. The core study coordination team consisting of the project leads and REACH will meet twice a month during the data collection period.

# 17. Finance and funding

We have been awarded a Barts Charity Research Seed Grant, which will cover all study-related costs. A summary of projected costings is as follows:

Category	Total

Staff	£0
Materials and Consumables	£12,700
Equipment	£1899
Public and Patient Involvement and Engagement + travel	£14,040
Publications/Dissemination	£4000
Animals	£0
Other	
GRAND TOTAL	£32,639

Contact details for our Funding Manager ([name]) are: [contact]

# 18. Insurance and indemnity

The insurance that Queen Mary has in place provides cover for the design and management of the study as well as "No Fault Compensation" for participants, which provides an indemnity to participants for negligent and non-negligent harm.

# 19. Dissemination of research findings

We have a number of plans for both academic and non-academic dissemination of research findings.

We anticipate at least three independent publications for submission to peer reviewed journals; a quantitative analysis main results from the primary objectives, the guideline review and a qualitative paper with analysis of the survey data. To further disseminate these we aim to present each of these arms at an appropriate conference e.g. the annual RCPCH conference or international neonatal conferences.

We will offer all study participants the study website details which will be updated with the study progress and results. We will also disseminate our findings on social media. These posts will focus on reaching the wider patient population in an accessible way, and will include summaries of the results from the qualitative branch of our study.

We anticipate that our findings will highlight disparities in care across the region and pave the way to discuss optimal clinical assessment and management of neonates with jaundice that is appropriate for babies of all skin tones. Our regional data may also guide future national studies.

## **Appendix 1: Summary of PPI scoping survey**

We received 32 responses from parents or carers with experience of postnatal care based within the London region. Many parents / carers understood newborn jaundice to be about "yellowing of the skin" and "elevated bilirubin". Parents mentioned yellowing of the eyes and problems with the liver as well as a need for it to be treated. Most parents (88%, n= 28/32) had experienced an infant they were caring for, being checked for or diagnosed with jaundice. There was a wide variation of self-identified ethnicity within this group, with 10 distinct ethnic groups as per the standardised NHS categories, and some choosing "any other". When asked whether they felt the baby's natural skin tone or ethnic background had any impact on this assessment, roughly a third said yes, a third said no and the remaining third wasn't sure (36%, 36% and 28% respectively). Themes they raised around this included:

- Feeling healthcare professionals had repeated misplaced concerns about their baby being jaundiced because of mixed race ethnicity;
- Jaundice investigations and treatments not being consented for or explained adequately.
- Baby's changing natural skin tone in the first days of life, affecting the ease in identifying jaundice.
- Paler babies appeared more jaundiced than they were, so investigated more.
- Difficulties identifying jaundice in some ethnicities over others.

When asked about how parents and healthcare professionals assess babies for jaundice, themes included:

- Many parents are aware that yellowing of the skin and eyes is a sign checked by both parents and HCPs.
- Others did not know how to identify jaundice and there were calls for better explanations and advice for parents on discharge and better trained community staff.
- There were some calls for universal jaundice screening.
- Concerns that the race of the parents or the baby may influence HCP management.
- Concerns over racial microaggressions from HCPs when describing jaundice in mixed race skin tones.

Most parents / carers said they would feel either neutral, comfortable or very comfortable with a healthcare professional using our skin tone / colour tool (94%). 2 parents were uncomfortable with it as they were concerned that the darkest skin tone group would not account for babies with the darkest natural skin tones, therefore missing an important group.

We have recognised this as a limitation of this tool, and noted that the number of darker skin babies in their original cohort was smaller than the lighter groups due to the limited skin colour variation in their original population. However, this is currently the only published validated neonatal skin colour tool, which is valuable seeing that neonatal skin has a notably different appearance from adult skin. There is an appreciable difference between the 4 skin colour groups, and we will be including all babies according to the group closest to their skin tone, as opposed to excluding those who do not perfectly match the pictures in a group. For example, any babies

with a natural skin tone darker than skin colour group 4, will be included within group 4, and any babies lighter than skin colour group 1, will be included within group 1.

#### Study Explanation Roleplay - Initial Reactions

- Parents found the study explanation clear and the communication approach considerate.
- Some parents were unaware that not all babies are checked for jaundice.
- It was suggested that the study team should clarify parents' understanding of their baby's jaundice check at the start of the conversation
- Parents felt flexibility in timing for discussions was important, given the nature of postnatal care.
- All parents felt they understood the explanation

## **Information Delivery & Materials**

- Parents noted overwhelming amount of paperwork at discharge makes it difficult to distinguish key information - make it clear this is for a research study and not part of health records
- Preference for verbal explanations first, followed by written materials.
- Suggestion to minimise reading content and clarify that the provided leaflet is for reference

#### Skin Tone Tool & Language Use

- Discussion around skin tone tool not covering all possible skin tones, worth highlighting we are categorising by closest match and conveying this clearly in PIS and conversation
- Some parents were uncertain about their baby's "natural" skin tone due to jaundice, suggested perhaps "expected skin tone". "Healthy skin tone" not a good alternative due to the connotation of baby being unhealthy.
- Parents agreed that the study team should assign skin tone categories for consistency, but consider how to address situation if parents disagree
- All parents found the language used acceptable and appropriately sensitive

#### Study Process & Practical Considerations

- Some parents wanted clearer expectations on timing—when assessments happen, how long they take, and who conducts them.
- Suggestion to move the discussion about jaundice to the beginning of the conversation.
- Preferred approach: Inform parents how long they have to read materials and specify how much time further steps will take.
- Need for clearer explanation about what data is collected from medical records, with brief examples to avoid it feeling vague or intrusive.

#### Participant Information Sheet (PIS)

• Generally well-received: clear, concise, and easy to understand.

- Suggested improvements:
  - o Clarify published data will be anonymous
  - o Consider translations for non-English speakers.
  - o Clearly caveat that skin tone tool does not cover all skin tones
  - Acknowledge that the skin tone tool is not fully representative of all skin tones.
  - o Potentially provide a one-page summary with visuals.

## Overall Acceptance of the Study

 All participants reported they would not opt out if they were approached for enrollment into this study

## Next Steps

- Adjust study materials to address feedback (e.g., clearer explanations, refined language, improved structuring of information).
- Develop a response plan for cases where parents disagree with skin tone categorisation
- Ensure clarity on data collection and timing expectations
- Participants were happy to be contacted for further input during data collection and results dissemination

# Appendix 3: focus group and semi-structured interview frameworks

## **Instruction for facilitators:**

The themes and questions below are guides for the discussion. Participants may wish to take the conversation in a different direction, but please ensure that you cover all of the themes listed.

# Focus group framework

#### Introduction for the group:

Thank you for coming today and agreeing to speak with us. Everything we discuss will be confidential. You have kindly agreed for us to make an audio recording and take notes of our discussion so in order to protect your privacy, we ask you not to mention your name (we shall assign you a pseudonym of your choice). We would like to learn a bit more about your experiences with newborn jaundice and how race or ethnicity can affect these.

Theme	Questions	Notes
Understanding of jaundice and experiences of assessment	
 
What was / is your understanding of newborn baby jaundice?         
 
a. Where did this information come from (e.g. your previous experiences, other family members, friends, own reading, healthcare professional guidance)
 
 
 
Tell us about your experiences with jaundice assessment.         
 
a. Either personal or when you have been made aware of neonatal jaundice otherwise.
 
 
 
	
Interactions between natural skin colour / race / ethnicity and the assessment of jaundice	
 
Was there anything that concerned you about how your baby was tested, or not?         
 
(e.g. delay in assessment / repeated unnecessary checks / uncertainty about diagnosis etc.)
 
 
 
Was there anything that concerned you about how your baby was treated or how you were kept informed, or not?
 
Did anything else contribute to this? (E.g. your healthcare professional's perceived ethnicity, their level of
 
	

	training, culture within the department, institutional racism, racial microaggressions etc.)	
Opinions on current jaundice guidelines e.g. NICE, BAPM, WHO.	Parents will be given excerpts from relevant guidelines regarding the consideration of race and ethnicity when assessing babies for jaundice.  1. What do you think about these recommendations?  a. Given variations in guidancewhat do you think about these different approaches (e.g. World Health Organisation (WHO) guidance for screening vs National Institute for Clinical Excellence (NICE) guidance not to screen).  2. Do you think any of the content needs to be modified or added to?  3. Do you think the wording is appropriate or should any of it be adjusted?  a. Discuss the Race and Health Observatory (RHO) recommendation that all guidelines should explicitly highlight limitations in visual assessment, especially in those from ethnic backgrounds.	

Empowering parents:
Parental education on jaundice, its detection and the deteriorating infant (RHO recommendation)

- 1. Were you given any information/ guidance on jaundice by healthcare professionals before or after your baby was born?
  - a. At which point were you given this?
  - b. When do you think it would have been most helpful?
  - c. Was it helpful / empowering in your parental role?
- 2. If given written materials, which were you given?
  - a. Were these easily accessible?
  - b. Were they representative of babies from a variety of ethnic backgrounds?
- 3. Which methods of education / advice did you find most helpful?
- If you were to co-design written materials for parents, what content would you include and how would they be presented? (e.g. webpages, Apps, online picture banks, videos on assessment etc)

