# Secondary Objective 3:

Free text answers from the parent survey and transcripts from focus groups and semi-structured interviews will be analysed using a thematic content approach consisting of six steps: familiarisation, coding, generating themes, reviewing themes, defining and naming themes, and writing up. This method will reduce confirmation bias when reviewing data. An inductive approach will be employed during familiarisation, to allow the data to determine themes and a latent approach will be used when analysing the data in order for the coding to consider the subtext and assumptions that may underlie the explicit content of the data. Qualitative manuscripts will utilise the Consolidated criteria for reporting qualitative research (COREQ) checklist.

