#### Semi-structured interview framework

#### **Interview Introduction:**

Thank you for coming today and agreeing to speak with us. Everything we discuss will be confidential. You have kindly agreed for us to make an audio recording and take notes of our discussion so in order to protect your privacy, we ask you not to mention your name (we shall assign you a pseudonym of your choice). We would like to learn a bit more about your experiences with newborn jaundice and how race or ethnicity can affect these.

Theme	Questions	Notes

	1. What was / is your	
Understanding of	understanding of newborn baby	
jaundice and	jaundice?	
experiences of	a. Where did this information	
assessment	come from (e.g. your previous	
	experiences, other family	
	members, friends, own	
	reading, healthcare	
	professional guidance)	
	2. Tell us about your experiences	
	with jaundice assessment.	
	a. Either personal or when you	
	have been made aware of	
	neonatal jaundice otherwise.	
	Was there anything that concerned	
Interactions between	you about how your baby was tested,	
natural skin colour /	or not?	
race / ethnicity and the	(e.g. delay in assessment / repeated	
assessment of jaundice	unnecessary checks / uncertainty about	
	diagnosis etc.)	
	Was there anything that concerned	
	you about how your baby was treated	
	or how you were kept informed, or	
	not?	
	3. Did anything else contribute to this?	
	(E.g. your healthcare professional's	
	perceived ethnicity, their level of	
	training, culture within the department,	
	institutional racism, racial	
	microaggressions etc.)	

Opinions on current jaundice guidelines e.g. NICE, BAPM, WHO.

Parents will be given excerpts from relevant guidelines regarding the consideration of race and ethnicity when assessing babies for jaundice.

- 1. What do you think about these recommendations?
  - a. Given variations in guidancewhat do you think about these different approaches (e.g. World Health Organisation (WHO) guidance for screening vs National Institute for Clinical Excellence (NICE) guidance not to screen).
- 2. Do you think any of the content needs to be modified or added to?
- 3. Do you think the wording is appropriate or should any of it be adjusted?
  - a. Discuss the Race and Health Observatory (RHO)
     recommendation that all guidelines should explicitly highlight limitations in visual assessment, especially in those from ethnic backgrounds.

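### The focus group and interview guides in Appendix 3 are mildly leading on race and ethnicity, and the safeguards in Section 10.2 act only after the data are collected

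*Protocol*

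**What the plan says.** Secondary Objective 3 (Section 6.2) and secondary endpoint 6 (Section 6.4) concern parents' opinions and experiences of the impact of skin tone or ethnicity on jaundice assessment. Section 8 lists the discussion topics in advance, and this is one of them.

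Appendix 3 gives the scripts. The focus group introduction reads: "We would like to learn a bit more about your experiences with newborn jaundice and how race or ethnicity can affect these". The interview introduction has the same framing: "newborn jaundice and how race or ethnicity can affect these". Facilitators are told that the questions are guides and that participants may steer elsewhere, but also: "please ensure that you cover all of the themes listed".

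Under the theme on skin colour, race and ethnicity, questions 1 and 2 ask whether anything about testing, treatment or information caused concern, or not. Question 3 asks whether anything else contributed. Its examples are the professional's perceived ethnicity and then their level of "training, culture within the department, institutional racism, racial microaggressions etc". The interview guide carries the same list, including "institutional racism, racial" microaggressions.

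On analysis, Section 10.2 (Secondary Objective 3) says of the six-step thematic approach: "This method will reduce confirmation bias when reviewing data". It adds that induction will be used during familiarisation "to allow the data to determine themes".

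**The concern.** Endpoint 6 asks what parents think about the influence of skin tone or ethnicity. To answer it credibly, a parent who saw no influence must find it as easy to say so as one who did. A session that opens on how race can matter, and then names particular forms of racism as possible contributors, tilts the conversation before the parent has been asked openly.

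The protocol's protection against bias sits later, in how transcripts are read. If a theme of institutional racism is then reported, a sceptical reader can ask whether parents raised it or the guide did, and the planned report would not separate the two. That would weaken a sensitive result which the study has good reason to want on firm ground. Section 19 states in advance that the team expects its findings to highlight disparities in care, which makes neutral collection more valuable.

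**Working it through.** No arithmetic settles this point. The check compares what is asked with what the analysis can correct.

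1. **Opening line.** Both scripts name race or ethnicity as something that can affect the parents' experience. The scoping survey in Appendix 1 asked instead whether skin tone or ethnic background had any impact. Its answers were 36% yes, 36% no and 28% unsure, from a survey with 32 responses. The protocol team has therefore already used a two-sided question and received two-sided answers.

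2. **Questions under the race theme.** Questions 1 and 2 do not mention race and allow the answer that nothing was of concern. The examples for the testing question (delay, repeated unnecessary checks, uncertainty about diagnosis) do not mention race either, and delay and excess checks point in opposite directions. Race first appears in the bracket under question 3. Of its five examples, three relate to race or ethnicity (perceived ethnicity, institutional racism, racial microaggressions) and two do not (level of training, departmental culture). No question asks whether skin tone or ethnicity had an impact.

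3. **Does another instrument ask it?** Other themes in the guides touch on ethnicity through guideline excerpts, the representativeness of leaflets and targeted screening, but do not ask about impact on the baby's own assessment. The parent survey (Table 2) has open items on rating and concerns, asks whether information covered natural skin tone, and asks what professionals should understand better about different skin tones. It too has no item on whether tone or ethnicity affected this assessment. Parents may volunteer it in free text, but direct questioning on endpoint 6 is left to the Appendix 3 sessions.

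4. **Where the safeguards act.** Section 10.2 ties the reduction of confirmation bias to reviewing data, and induction to familiarisation. Both come after the session. They govern how a remark is coded and cannot make a prompted remark spontaneous. Sessions are audio-recorded and transcribed (Section 13.1), so the order of prompt and answer can be recovered, but no step to use it is described.

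5. **Reach.** Section 8 plans groups of 4 to 6 on about 2 occasions: 2 × 4 = 8 to 2 × 6 = 12 parents, plus interviews whose number is not given. In a group, every participant hears whatever prompt is used.

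**The case against.** The strongest reply is that this is ordinary semi-structured practice. Secondary Objective 3 requires the topic to be raised, so pre-set topics and an instruction to cover them are legitimate. Both guides begin with open questions on understanding and experience, the guide allows departure, and nothing says that the bracketed examples must be read aloud. Section 5.2 says the scoping survey informed the session themes, and in Appendix 1 parents themselves raised racial microaggressions, race influencing management, and better staff training. Parent representatives have a role in the content (Section 12). Survey free text enters the same analysis without passing through these scripts.

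Most of this stands, and it rules out several stronger readings that a reader might infer:

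- That the scripts tell parents race affects jaundice care. They say it *can* affect their experience.
- That the facilitator supplies the themes. Discussion topics are pre-set, but analytic themes are still coded from the data.
- That the examples all point one way. Two of the five are neutral.
- That Section 10.2 contradicts Appendix 3. Its claims are limited to familiarisation and data review.
- That prompted and volunteered remarks cannot be told apart. The transcripts allow it.

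What the reply does not answer is that the introduction leans one way, that institutional racism is a loaded example absent from the parents' themes reported in Appendix 1, and that the two-sided question on impact is never asked.

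**Conclusion.** The point holds in a limited form. One introductory sentence, used in both scripts, and part of one example list are mildly leading on secondary endpoint 6. No neutral question on impact offsets them, and the analysis safeguards do not reach data collection.

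The size of any distortion cannot be derived from the protocol. The scoping split should not be read as showing that about two thirds of study parents would meet a script presuming the opposite of their view: it comes from a small pre-study survey, and an unsure parent is not contradicted by the words *can affect*. Nor do the documents support a forecast that a theme of institutional racism will appear regardless of what parents think.

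The conclusion assumes that facilitators deliver the introduction as written and at least sometimes use the bracketed examples. If the examples are never voiced, only the introduction and the missing question remain. The primary objectives, the sample size and the other secondary endpoints are unaffected. This is a low-cost improvement to the qualitative arm.

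**What to change.** Amend Appendix 3, in both frameworks:

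- Replace the introduction with a neutral one about the parent's experience of their baby's jaundice assessment.
- Under the race/ethnicity theme, add an open, two-sided question: whether the baby's skin tone or ethnic background had any impact, or none, on the assessment. This follows the scoping survey's own question.
- Move the bracketed examples to a probe list, with an instruction to use them only after the open answer. Balance the list, for instance with the scoping-survey theme that paler babies looked more jaundiced than they were and were tested more.

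In the analysis for Secondary Objective 3, mark each relevant extract from the transcripts as spontaneous or prompted, and make the distinction visible when themes are reported.

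The cost is rewording one appendix, one additional code and slightly longer sessions. The parent representatives already in the team can review the wording. No additional participants are needed.
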